RSV infections result in high rates of hospitalization in infants, a large disease burden among infants and young children, and excess mortality in the elderly [Graham, 2011]. RSV infects 50-70% of infants during the first year of life and essentially all children will have had an RSV infection by their third birthday [Hall, 2004]. In the early months of life, infants may have protection against RSV through the maternal antibodies transferred to them during pregnancy. High titers of maternally derived RSV-neutralizing antibodies [Roca, 2002] have been shown to be inversely associated with the incidence of RSV associated-acute LRTI during the first 6 months of life, whereas incomplete transfer of maternally derived RSV-neutralizing antibodies has been implicated in the increased risk of severe RSV infection in preterm infants [de Sierra, 1993]. Previous infection with RSV does not prevent subsequent infections. Therefore, re-infection with RSV occurs throughout an individual's lifetime and is common in all age groups [Simoes, 1999; Krilov, 2011].

Globally, it is estimated that in children below 5 years of age, RSV causes >30 million acute lower respiratory infections (LRTI) each year resulting in more than 3 million hospitalizations, making it the most common cause of hospitalization for LRTI or all cause from any single pathogen in this age group [Nair, 2010]. RSV is the most common cause of bronchiolitis and pneumonia in children less than 1 year of age worldwide, with

highest risk in children less than 6 months of age [Nair, 2010; Langley, 2011]. A United States (US) based study conducted in children less than 18 years of age, found RSV in 58% of the hospitalizations for LRTI compared to parainfluenza virus 1-3 in 17%, influenza A/B in 21%, adenovirus in 2% and rhinovirus in 2% [Henrickson, 2004]. On a community level, a US day-care based study assessing the causes of respiratory tract infection (RTI) in children less than 1 year of age found that RSV infection was present in 11% of the cases, compared to rhinovirus in 35%, adenovirus in 22%, human coronavirus in 15%, parainfluenzavirus in 12%, human meta-pneumovirus in 4% and influenza A in 2% [Fairchok, 2010]. This difference between community and hospital proportions of RSV related infections indicates the propensity of RSV to cause more serious cases of RTI, mainly LRTI, compared to other viruses.

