The measured maternal antibody levels by storage condition or tube type will be analysed graphically and by group statistics (mean, 95% CI). Group means will be compared by t-test to assess the statistical significance of differences.

The measured maternal antibody levels in samples collected 'according to recommended procedure' and 'not according to recommended procedure' will be analysed graphically and by group statistics (mean, 95% CI). Group means will be compared by t-test to assess the statistical significance of any difference.

• To assess the impact of potential RSV risk factors (e.g. complications at birth, family history of respiratory disease, lifestyle characteristics and household composition, breast feeding, passive smoking, day care attendance) on the incidence and severity of RSV-associated LRTI.

The incidence of any, severe, non-severe RSV-associated LRTI will be analysed using a Poisson regression model including potential risk factors.

• To assess the natural decay of maternal antibody levels using a single follow-up blood sample collected from a randomly selected sub-cohort of subjects at 2, 4, 6, 12, 18 and 24 months.

The primary analysis will be based on ATP sub-cohort for this objective.

The decay of maternal antibody levels over time will be analysed graphically and by a log-linear regression. A true, natural decay curve will be explored by stochastically reducing the sample to uninfected subjects only. The following steps will be taken to identify, confirmed and suspected infected subjects to eliminate these from the sample;

- Subjects with an RSV positive nasal swab during the study before time of sampling will be eliminated.
- A sensitivity analysis of the decay curve will be explored in sub-sample consisting of the subjects born 'off-season' as these have the lowest likelihood of having been infected.
- Subjects with an antibody titer at the sampling time that is more than 2-fold above the expected value based on their baseline (cord blood) value and the established decay curve will be considered to have been infected, eliminated and the decay curve refined.
- Step 3 is repeated up to 5 times until the most accurate decay curve is established.

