- The recruitment will be performed using a first application of SBIR where subjects will be entered on obtaining ICF and recruitment is controlled on the monthly recruitment rate. The aim is to attain a reasonably stable number of subjects per month over the full recruitment period in order to achieve an equal spread in the age of subjects at first exposure to an RSV season. Recruitment will be actively controlled through the SBIR system on country level according to agreed targets, actual recruitment rates, and further recruitment potential, so as to achieve a sufficient population on a regional level. With concurrent recruitment across the globe (with different seasonality) and an intended, steady recruitment over 18 months, the following population is to be included;
 - Subjects from NH during first 6 months
 - Subjects from SH during first 6 months
 - Subjects from NH during second 6 months
 - Subjects from SH during second 6 months
 - Subjects from NH during third 6 months; repeat of first 6 months NH
 - Subjects from SH during third 6 months; repeat of first 6 months SH

 In case recruitment is extended beyond 18 months, subjects recruited in the fourth 6 month period are a repeat to those recruited during the second 6 month period

Figure 3 RSV seasons in Northern and Southern Hemispheres

NH=Northern hemisphere, SH=Southern Hemisphere. Figure assumes equal recruitment targets on both hemispheres (which is not a requirement for the study).

Figure A represents recruitment in the NH and assumes RSV seasons running from November to April relative to a currently estimated time point 0 in Nov 2013.

Figure B represents recruitment in the SH and assumed RSV seasons running from May to October relative to a currently estimated time point 0 in Nov 2013.

Recruitment on both Hemispheres will include a period of 'On Season' recruitment and a period of 'Off Season' recruitment and a third period of recruitment matching the first period.

An interim analysis data lock is scheduled after 1.5 years or in June 2015, whichever occurs first.

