6.1.4.5. Time of birth relative to the transmission season

The transmission season period is defined:

- from April to September in the North hemisphere
- from October to March in the South hemisphere
- all year long in the tropical hemisphere

A summary of transmission season is displayed in the following table.

200150 (EPI-RSV-005 BOD)

				,
Statistical	Analysis	Plan	Amendment	1 Final

Country	Hemisphere	Transmission season period
Canada	North hemisphere	April 1 to September 30
United States	North hemisphere	April 1 to September 30
Finland	North hemisphere	April 1 to September 30
Argentina	South hemisphere	October 1 to March 31
South Africa	South hemisphere	October 1 to March 31
Thailand	Tropical hemisphere	All year long
Bangladesh	Tropical hemisphere	All year long
Honduras	Tropical hemisphere	All year long

Table 10Summary of transmission season by country

All subjects from tropical hemisphere will be considered to be born within the season.

Subjects from North hemisphere will be considered to be born within the season if they are born between April and September. Subjects from South hemisphere will be considered to be born within the season if they are born between October to March.

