6.9.3. Analysis of tertiary objective: natural decay of maternal neutralizing antibodies

The analysis will be based on total sub-cohort subject with blood sampling at month 2, 4, 6, and 12 for this objective.

The decay of maternal antibody levels over time will be analysed graphically and by a linear regression of the log of maternal antibody levels. A true, natural decay curve will be explored by stochastically reducing the sample to uninfected subjects only. The following steps will be taken to identify, confirmed and suspected infected subjects to eliminate these from the sample;

STEP 1: Subjects with an RSV positive *nasal swab* during the study before time of sampling will be eliminated. Note that such subjects are removed from the analysis because they are infected by RSV; as a consequence their antibody levels are no longer maternal antibody levels.

STEP 2: Run the model and compute expected value based on the decay curve for each subjects

200150 (EPI-RSV-005 BOD)

Statistical Analysis Plan Amendment 1 Final

STEP 3: Subjects with an antibody titer at the sampling time that is more than 2-fold above the expected value based on their baseline (cord blood) value and the established decay curve will be considered to have been infected, eliminated and the decay curve refined.

STEP 4: Step 3 is repeated up to 5 times until the most accurate decay curve is established.

The natural decay of antibody will be determined using linear regression between the log of antibody level (Y) and time t (age in months) with subject as a random effect. Indeed, all subjects have RSV neutralizing antibodies measured at birth (cord blood). And, each subject of the Total sub-cohort will be randomly selected to be sampled for RSV neutralizing antibodies at one of the following time points: 2, 4, 6, and 12 months. For the natural decay model, subjects will have maximum 2 RSV neutralizing antibodies measures, one at birth and one either at 2 months or 4 or 6 or 12 months.

A table will describe the decay rate and half-life statistics of the natural decay model.

A descriptive table will describe the serology status (positive/negative) according to the natural decay analysis.

A sensitivity analysis of the decay curve will be explored in sub-sample consisting of the subjects born 'off-season' as these have the lowest likelihood of having been infected.

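### Restricting the antibody decay curve to off-season births lowers RSV exposure only at the month 2 and month 4 draws, so the check says little about contamination at months 6 and 12, which dominate the fitted slope.

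*Protocol*

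**What the plan says.** The protocol's tertiary decay objective uses a "single follow-up blood sample collected from a randomly selected sub-cohort of subjects at 2, 4, 6, 12, 18 and 24 months" (section 9.7.3). The SAP narrows the model: "The analysis will be based on total sub-cohort subject with blood sampling at month 2, 4, 6, and 12 for this objective" (section 6.9.3). It fits log titre on age with a subject random effect, using cord blood and one later draw per child.

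Children with an RSV-positive swab before the draw are removed first. Children whose titre is more than 2-fold above the expected value are then removed, in up to five rounds. Separately, the SAP says: "A sensitivity analysis of the decay curve will be explored in sub-sample consisting of the subjects born 'off-season", for the reason the protocol gives, "as these have the lowest likelihood of having been infected". No draw age is attached to that reason in either document.

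Two sets of season dates are in play. Protocol Appendix C "assumes RSV seasons running from November to April" for the Northern Hemisphere and "assumed RSV seasons running from May to October" for the Southern. SAP 6.1.4.5 and Table 10 give April to September for the north and October to March for the south. The SAP adds: "All subjects from tropical hemisphere will be considered to be born within the season".

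**The concern.** Season of birth predicts how much RSV a child has met only while the child is young. By the first birthday everyone has lived through a full season, whatever the month of birth. A restriction on birth season can therefore leave the infected share unchanged at the later draws, where infection has had most time to accumulate.

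The decay curve also matters beyond its tertiary objective. SAP Table 9 and section 6.9.2 use its expected titre to classify infection at months 2, 4, 6 and 12, which is a secondary objective. If residual infection flattens the curve, expected titres are too high and prevalence is understated. A sensitivity analysis that cannot move at the influential ages might agree with the main curve whether or not that has happened.

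**Working it through.** The plan gives no exposure figure to reproduce, so the check computes in-season time between birth and draw.

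**Inputs**
- 6-month season and steady monthly recruitment: protocol Appendix C.
- Draws allocated at months 2, 4, 6 and 12: 200, 200, 250 and 300 (protocol Table 1, SAP Table 1), total 950.
- First-year infection: "RSV infects 50-70% of infants during the first year of life" (protocol 1.1.1).
- Assumptions: births uniform over the year, flat risk in season, none outside it, ±1 week draw window ignored.

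**In-season months by age a (a ≤ 6)**
- Off-season birth at time t after the off-season starts: max(0, t + a − 6). Averaged over t from 0 to 6, this is a²/12.
- In-season birth: min(a, season left). The average is a − a²/12.
- At a = 12 every child has 6, because any 12 months contain one full season.

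| Draw | Off-season births | In-season births |
|---|---|---|
| Month 2 | 4/12 = 0.33 | 2 − 0.33 = 1.67 |
| Month 4 | 16/12 = 1.33 | 4 − 1.33 = 2.67 |
| Month 6 | 36/12 = 3.0 | 6 − 3.0 = 3.0 |
| Month 12 | 6.0 | 6.0 |

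The 5-month southern season of protocol 1.1.1 gives 2.5 vs 2.5 at month 6 and 5.0 vs 5.0 at month 12.

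**Cumulative infection, before any elimination step.** Set the in-season hazard h so that 1 − exp(−6h) is 50% or 70%, giving h = 0.116 or 0.201. Off-season vs in-season births:
- month 2: 4-6% vs 17-28%
- month 4: 13-21% vs 26-39%
- month 6: 28-42% in both. For the 50% case, 1 − 0.5/0.693 = 0.28; for the 70% case, 1 − 0.7/1.204 = 0.42
- month 12: 50-70% in both

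**Weight of the late draws**
- By count: (250 + 300)/950 = 58%.
- High within-child correlation: information on the slope is proportional to n·a², that is 800, 3,200, 9,000 and 43,200, total 56,200. Months 6 and 12 supply 52,200/56,200 = 93%, and month 12 alone 77%.
- Zero correlation: the overall mean age is 6,300/1,900 = 3.32 months. The sums of squares, cord sample included, give 86% for months 6 and 12 and 73% for month 12 alone. Intermediate correlations fall between these values.

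**Uneven births.** The synopsis takes serum from the first 2000 enrolled (Table 6 gives 2400). At 2400/18 = 133 per month, 2000 takes 15 months. From a November start, November-January births then count twice. Month 6 becomes 3.0 vs 3.5 in the north, since (2×13.5 + 4.5)/9 = 3.5 for in-season births. In the south it becomes 2.5 vs 3.0, since (2×4.5 + 13.5)/9 = 2.5 for off-season births. Month 12 does not change.

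**If off-season follows SAP Table 10.** Measured against the protocol's 6-month seasons, the children labelled off-season are the more exposed: 1.7-1.8 vs 0.2-0.3 months at month 2, and 2.7-3.2 vs 0.8-1.3 at month 4.

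**The case against.** The strongest reply is that the check does work at months 2 and 4. There, off-season births have one fifth and one half of the in-season group's exposure, and those draws are 400 of 950 (42%). That stands. A reader might infer that the analysis cannot detect contamination at all, and the figures do not support that. They do show that the early draws supply only about 7-14% of the information on the single slope, so a difference confined to them would barely move the fitted rate.

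Second, equality at month 6 is an average under even births. Individual exposure runs from 0 to 6 months, and the staggered sub-cohort gives off-season births about half a month less. This also stands. Only month 12 is equal for every child.

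Third, the 28-42% and 50-70% shares might be read as contamination left in the curve. They are cumulative infection before the swab exclusion and the 2-fold trimming, and the documents do not allow the residual to be calculated. Those two steps have limits. Swabs are taken only at examination visits, SAP Table 4 notes that surveillance was not designed to find asymptomatic RSV, and the trimming is judged against the fitted curve itself.

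Fourth, this is an exploratory check on a tertiary objective in a descriptive study, and SAP 6.9.3 allows the decay analysis to be adapted. Reported prevalence comes from the main curve, so changing the sub-sample alters no reported prevalence figure. That is correct; what is lost is a usable warning about the curve.

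**Conclusion.** The concern holds in limited form. The off-season restriction reduces exposure at months 2 and 4. It gives no reduction at month 12, and none on average at month 6 with even births (about half a month under the 15-month enrolment pattern). The reason given for it is therefore not true for 550 of the 950 allocated children (58%), whose draws supply about 86-93% of the slope information. Agreement between the two curves would be weak evidence about contamination at months 6 and 12. It does not follow that the main curve is biased, nor that the reported prevalence is wrong.

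The exposure result rests on a season of about six months, near-uniform births and negligible off-season risk. The month 12 result needs only a season that recurs yearly. The weighting assumes the planned allocation and ignores drop-out and eliminations.

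The conflict over season dates comes first. If SAP Table 10 defines off-season, the sub-sample is the more exposed group at the two draws where the check could have worked. This is a change worth making, not one on which the primary results depend.

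**What to change.** 1. Reconcile the SAP Table 10 transmission seasons with protocol 1.1.1 and Appendix C. This must come first. With Table 10 as it stands, a rule of no in-season time before the draw would keep northern births from October to January at month 2. Against a November-April season they have lived (1.5 + 2 + 2 + 2)/4, about 1.9 of 2 months, in season. At month 4 it would keep October-November births, with (3.5 + 4)/2 = 3.75 of 4 months.
2. In protocol 9.7.3 and SAP 6.9.3, define the sub-sample by in-season time between birth and draw: none for month 2 and month 4 samples, and at most 1 month for month 6 samples.
3. Fit the sensitivity curve on months 2-6 and compare it with the main model refitted on months 2-6, so that both cover the same ages.
4. State that no low-exposure subset exists at month 12.

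The change needs only birth date, draw date and country season, which are already held. The cost is size. Assuming equal enrolment across the eight countries, five of them temperate, and before drop-out and swab exclusions:
- month 2: 200 × 5/8 × 1/2 × 2/3 ≈ 42 children
- month 4: 200 × 5/8 × 1/2 × 1/3 ≈ 21
- month 6: 250 × 5/8 × 1/6 ≈ 26 (one sixth of off-season births, and the same share of late in-season births)

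Thailand, Bangladesh and Honduras still drop out, because their season is set as all year. The check would therefore support only the temperate-country decay rate, and the report should say so.

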9.8. Analysis of Objectives for the Extension study

9.8.1. Primary objectives: none

9.8.2. Secondary objectives

Data for secondary endpoints may be pooled across the primary and extension periods. Additional details are provided in the SAP.

9.8.2.1. To determine the population attributable risk of wheeze and asthma from birth to sixth birthday due to RSV clinical LRTI in the first two years of life.

The incidence rate of medically attended wheeze, wheeze or asthma requiring hospital admission, and prescription of medications for wheeze or asthma may be calculated and stratified by country.

The population attributable risk *may be* calculated by subtracting the incidence rate in the subjects who did not have RSV clinical LRTI in the first two years of life from the incidence rate in all subjects including both who had and who did not have RSV clinical LRTI in the first two years of life.

Details will be provided in the SAP. An example follows.

The population attributable risk of medically attended wheeze may be calculated as:

Ip-Iu

Where Iu is the incidence rate of medically attended wheeze in subjects who did not have RSV clinical LRTI in the first two years of life, and Ip is the incidence rate of medically attended wheeze in all subjects including both who had and who did not have RSV clinical LRTI in the first two years of life. *The above population attributable risk formula may be further adapted to best accommodate the data and their required analytic assumptions (e.g., a modified formula may be used for population attributable risk calculations involving recurrent outcomes).*

9.8.2.2. To determine the population attributable risk percent of wheeze and asthma from birth until sixth birthday due to RSV clinical LRTI in the first two years of life.

The population attributable risk percent together with 95% CI of medically attended wheeze, wheeze or asthma requiring *hospital* admission, and prescription of medications for wheeze and asthma *may* be calculated overall and by age strata (0-2 years, 2-4 years and 5-6 years), respectively.

The population attributable risk percent *may be* calculated by dividing the population attributable risk by the incidence rate in all the subjects including both who had and who did not have RSV clinical LRTI in the first two years of life.

For example, the population attributable risk percent of medically attended wheeze *may* be calculated as:

(Ip-Iu)/Ip*100

Where Iu is the incidence rate of medically attended wheeze in subjects who did not have RSV clinical LRTI in the first two years of life, and Ip is the incidence rate of medically attended wheeze in all subjects including both who had and who did not have RSV clinical LRTI in the first two years of life. *As with the population attributable risk, the above formula may be adapted, as appropriate, to best suit the data*.

The detail for calculating the CI for both population attributable risks and population attributable risk *percent* will be provided in the *SAP*.

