1.1.2. Asthma

Infant respiratory viral infection and childhood asthma are the most common acute and chronic diseases of childhood, respectively. Common clinical features and links between these diseases have long been recognized, with early-life RSV LRTIs being strongly associated with increased asthma risk.

Although asthma is probably a heterogeneous disease or syndrome, three factors and/or events consistently emerge for their ability to significantly influence asthma inception in the first decade of life: immune response aberrations, which appear to be defined best by the concept of cytokine dysregulation; LRTIs, in particular RSV; and some form of gene–environment interaction that needs to occur at a critical timeperiod in the development of the immune system or the lung [Lemanske, 2002].

Population-level contribution of RSV LRTIs is best demonstrated by the populationattributable risk for asthma after these early-life LRTIs. Among infants, the cumulative incidence of LRTI is approximately 18 to 32% in the first year of life and approximately 9 to 17% in the second year of life. Among infants with LRTI, the prevalence of RSV can be as high as 80%, especially in the first 3 months of life. Thus, the phenotype of asthma after infant RSV LRTI accounts for up to 31% of early childhood asthma, with a population-attributable risk estimated at about 13% in several diverse populations [Feldman, 2015].

Numerous longitudinal studies have demonstrated this first important line of evidence that RSV LRTIs precede the development of asthma. Several birth cohort studies also demonstrate a dose–response relationship between infant respiratory viral infection severity and asthma risk, with increasing infant infection severity associated with greater childhood asthma risk and asthma severity [Feldman, 2015].

The Childhood Origins of Asthma (COAST) study was developed to determine and define the importance of these three factors on asthma pathogenesis and to test different asthma case classifications [Lemanske, 2002; Lemanske, 2005; Bisgaard, 2011; Jackson, 2008; Jackson, 2012; Bønnelykke, 2015]. These studies have used similar albeit slightly different case definitions on asthma diagnosis. The International Study of Asthma and Allergies in Childhood (ISAAC) takes a slightly different parentbased questionnaire approach toward assessing asthma prevalence in young children.

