9.8.3. Tertiary objectives

9.8.3.1. To explore the association of RSV clinical LRTI in the first two years of life and other potential risk factors for wheeze and asthma

Endpoints such as medically attended wheeze, wheeze or asthma requiring *hospital* admission, and prescription of medications for wheeze or asthma *may be calculated as recurrent events and* stratified by country.

Occurrence/recurrence rates will be calculated overall and by subgroups *for each of the outcomes, as relevant.* Multivaria*ble* Poisson regression *or other appropriate* models

including RSV clinical LRTI in the first two years of life and other potential risk factors such as, but not limited to, family history of asthma, and/or allergies, contact with pets, child history of allergy, eczema or atopic dermatitis, etc., will be explored, respectively.

9.8.3.2. To explore the performance of asthma case definitions.

The number and percentage of children with diagnosis of asthma (case definitions 1, 2, *and 3* will be described for each *applicable* age; the number and percentage of children with recurrent wheeze *at each applicable age* will be described overall and by country in frequency tables.

The risk of asthma at the age of 6 years using case definitions 1, 2 and 3 (occurring from 2^{nd} to the 6th birthday) will be analyzed using multivaria**ble** logistic regression model including RSV clinical LRTI in the first two years of life and other potential risk factors listed above, respectively.

- Statistical analysis of agreement will be performed to compare *asthma* case definitions *1*, *2*, *and 3 to each other*.
- Cohen's kappa *(or other appropriate)* coefficient *may be used for the comparisons*. The magnitude of the kappa coefficient represents the proportion of agreement greater than that expected by chance.

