9. CHANGES FROM PLANNED ANALYSES

- Due to the number of subjects with examination visit but without surveillance visit:
 - RSV LRTI endpoints computed using data from examination visit were added to the endpoint RSV-associated RTI with a suspicion of involvement of the lower respiratory tract definition computed using data from surveillance visit
 - The delay between LRTI identification and swab sample is not considered in the case definition
 - The subgroup analysis by collection time of swabs (72 hours/48 hours from the start date of the case (date of the call), 72 hours/48 hours from the reported onset of symptoms) has been removed
- In protocol it is suggested to analyse by country and then pool by hemisphere and region. Pooling across such diverse settings is not developing strong messages about RSV incidence and therefore we limit our subgroup analysis to by country. Where the protocol described overall incidence we have preferred to only do pooled incidence across countries by year of life. This aids meaningful interpretation and minimises tables.
- In the analysis of the key healthcare utilization and health outcomes: the hospitalization status, intensive care unit attendance, clinical diagnosis of bronchiolitis or pneumonia, death has been replaced by: outpatient visit, emergency Room visit, inpatient Admission (non intensive care), innpatient Admission (intensive care), no consultation other than site clinic and other.
- In the analysis of the performance of case definition, the key health outcome does not include intensive care unit attendance, clinical diagnosis of bronchiolitis or pneumonia and death. Instead, hospitalization status according to WHO, GSK, Nokes, and exploratory case definition will be used for the analysis.
- The incidence rates of RSV-associated LRTI/severe LRTI as classified by the GSK and Nokes case definition are not computed.
- Incidence rate of all cause RTI provided instead of per protocol non-RSV associated RTIs as RSV RTIs are subset of all cause RTI. Hence analysis of all cause RTIs is more relevant and conventional in epidemiological studies.
- Descriptive statistics of the different types of healthcare utilization will not be provided among non-RSV-associated RTI with a suspicion of involvement of the lower respiratory tract, overall and by subgroups.

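### The extension's attributable risk of wheeze and asthma is specified only as a crude contrast; no adjustment for country or other confounders is pre-specified for it.

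*Protocol*

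**What the plan says.** - **PAR (Protocol 9.8.2.1).** Described as "subtracting the incidence rate in the subjects who did not have RSV clinical LRTI in the first two years of life from the incidence rate" for the whole cohort, that is Ip − Iu.
- **PAR% (Protocol 9.8.2.2).** (Ip − Iu)/Ip × 100, which may "be calculated overall and by age strata (0-2 years, 2-4 years and 5-6 years".
- **Country.** The same section says the incidence rates of medically attended wheeze, hospital admission and "prescription of medications for wheeze or asthma may be calculated and stratified by country". No rule turns these into country-specific PARs or combines them.
- **Room to change.** The "population attributable risk formula may be further adapted to best accommodate the data and their required analytic assumptions", with recurrent outcomes as the only example; for PAR%, "the above formula may be adapted, as appropriate, to best suit the data". Neither statement mentions confounding.
- **Adjusted models.** Protocol 9.8.3.1 plans multivariable Poisson (or other) regression with RSV LRTI and "other potential risk factors such as, but not limited to, family history of asthma, and/or allergies, contact with pets", and 9.8.3.2 plans logistic regression for asthma. Both serve tertiary objectives, and neither is said to supply the PAR.
- **SAP.** The protocol leaves PAR details and confidence intervals to the SAP. The supplied SAP (end of section 2.1) states that it does not cover the extension analyses.
- **Meaning of the PAR.** The protocol glossary defines it as the incidence that would disappear if the exposure were removed.

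**The concern.** The extension has no primary objective, and PAR and PAR% are its only secondary objectives (Protocol 2.2). Protocol 1.2 says the results may be used to judge the public health impact of a future vaccine. That use needs the causal quantity in the glossary. A crude contrast delivers it only if children with and without RSV LRTI would otherwise have had the same wheeze rate.

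The documents themselves give reasons to doubt that. SAP 6.6.3 lists country of birth and a first-degree relative with asthma as candidate risk factors for RSV LRTI, the exposure. Protocol 9.8.3.1 lists family history of asthma as a candidate risk factor for wheeze, the outcome. Protocol 1.1.1 says that practice and access influence who is hospitalised, and 1.1.2 says that local practice affects the diagnosis of asthma and the management of wheeze; admission and prescribing are both PAR endpoints. Protocol 3.2.1 says confounder data are collected so that analyses can be adjusted, but the PAR section does not take this up. The problem remains even if only wheeze after age 2 is counted.

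**Working it through.** **1. The protocol's own benchmark.** Protocol 1.1.2 describes asthma after RSV LRTI "with a population-attributable risk estimated at about 13% in several diverse populations", and puts asthma following RSV LRTI at up to 31% of early childhood asthma. No relative risk is given, so the 13% can only be checked for consistency. From PAR% = pc(1 − 1/RR): 0.13 = 0.31(1 − 1/RR) gives RR = 1.72. Exposure prevalence is then p = 0.31/(1.72 × 0.87) = 20.7%. This lies within the 14.4% to 25.6% implied for year 1 by the same section (LRTI 18% to 32%, RSV share up to 80%).

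**2. Bias when RSV has no effect.** Let stratum exposure be e and stratum wheeze rate w, independent within stratum. Then Iu = mean[(1 − e)w]/(1 − ē) = w̄ − cov(e,w)/(1 − ē), so

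crude PAR% = cov(e,w)/[(1 − ē) w̄].

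It is zero only if e and w are uncorrelated across strata, and it takes the sign of that correlation. A PAR computed within strata and then combined is 0% on the same data.

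**3. Two equal country groups.** All inputs are assumptions; the documents give no country-level wheeze rates.

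| RSV LRTI | Wheeze | Ip | Iu | Crude PAR% |
|---|---|---|---|---|
| 10%, 20% | 10%, 20% | 0.150 | (0.9×0.10 + 0.8×0.20)/1.7 = 0.147 | 2.0 |
| 10%, 30% | 10%, 30% | 0.200 | (0.9×0.10 + 0.7×0.30)/1.6 = 0.1875 | 6.3 |
| 10%, 40% | 5%, 30% | 0.175 | (0.9×0.05 + 0.6×0.30)/1.5 = 0.150 | 14.3 |
| 10%, 40% | 30%, 5% | 0.175 | (0.9×0.30 + 0.6×0.05)/1.5 = 0.200 | −14.3 |

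**4. A spread taken from the documents.** The hospitalisation rates at 0-5 months in Protocol 9.3 run from 16.9 to 44.1 per 1000, a ratio of 2.6. This is only a guide, since the exposure here is RSV LRTI of any severity. With mean exposure 20.7% and two equal groups, exposure is 11.5% and 29.9%. Assumed wheeze ratios of 2, 3 and 5 give crude PAR% of 3.9, 5.8 and 7.7. The ceiling, as the wheeze ratio grows without limit, is (0.299 − 0.207)/(1 − 0.207) = 11.6%.

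**5. An individual-level confounder.** Assume family history in 20% of children, exposure 15% without it, exposure ratio 1.5 to 2 and wheeze ratio 2 to 3. The lower end is 0.2×0.8×0.075×1/(0.835×1.2) = 1.2 points; the upper end is 0.2×0.8×0.15×2/(0.82×1.4) = 4.2 points.

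**6. Country and one individual confounder together** (confounder prevalence 30%, mean exposure 20.7%, effects multiplicative). Country ratios of 2 for exposure and 2 for wheeze, with confounder ratios of 1.5 and 2, give 4.9%. Country ratios of 2.6 and 3, with confounder ratios of 2 and 3, give 12.2%.

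**The case against.** The strongest reply is that nothing is fixed. The section says the PAR may be calculated this way, presents the formula as an example, allows adaptation and points to the SAP. Country-stratified rates are allowed, and country PARs could be formed from them. All analyses are descriptive (Protocol 9.9), the objectives speak of association, and a separate extension SAP may exist.

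Much of this stands, and it limits the point to what is pre-specified. It does not close the gap. The only named adaptation is for recurrent outcomes, and a general permission leaves the choice of confounders until after the data are seen. A descriptive label also sits badly with the causal glossary definition and with the 9.8.2 headings, which attribute wheeze and asthma to RSV LRTI.

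Three stronger readings are tempting but unsupported:

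- **That the PAR will be pooled over eight countries.** Eight is the primary-study list in SAP 6.3. Extension enrolment is limited to participating sites (Protocol 5.3.2), and the number of extension countries is not stated.
- **That the sponsor has already rejected such pooling.** The SAP section 9 remark, "Pooling across such diverse settings is not developing strong messages about RSV incidence", explains why subgroup analysis of primary-study RSV incidence was limited to country. It shows caution about pooling but says nothing about how the extension PAR will be computed.
- **That confounding alone would produce the literature value.** In step 3 only the 4-fold and 6-fold case passes 13%. At the 2.6-fold spread with equal groups, country alone cannot pass 11.6%. If the high-risk group were 25% of children, 13% would still need a 6.5-fold wheeze ratio. The 13% also refers to asthma, whereas the PAR endpoints are medically attended wheeze, admission and prescriptions.

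**Conclusion.** The point holds as a gap in pre-specification. The two documents give only crude formulas for the extension's sole secondary objectives and attach no confounding adjustment to them. Followed as written, they do not estimate the glossary's quantity when RSV LRTI and wheeze vary together across countries or risk groups.

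With no RSV effect, the bias in PAR% is about 2 to 6 points for aligned 2- to 3-fold spreads in both across two equal country groups. It is 14 points only with a 4-fold exposure and 6-fold wheeze spread, and −14 points if those gradients oppose. The size rests on assumed spreads and group shares, and the documents do not show which way the country gradients run. A reader might infer that the crude PAR% will be inflated up to the literature figure; neither that size nor that direction is established. Whether an extension SAP already contains adjustment cannot be judged from these documents.

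**What to change.** Pre-specify in the extension SAP that the main PAR and PAR% are country-standardised and covariate-adjusted:

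- Fit the Poisson model of Protocol 9.8.3.1 with country always included, plus pre-exposure factors: gestational age, family history of asthma or allergy, smoke exposure, household composition and day-care, and season of birth.
- Predict each child's rate with RSV LRTI as observed and again with it set to absent. PAR is the mean difference; PAR% is that difference divided by the observed rate. With no interaction involving RSV LRTI, pc(1 − 1/adjusted RR) is an equivalent option, where pc is the share of events in children with RSV LRTI.
- Take the confidence interval from the delta method, or from a bootstrap of children within country or site. Resampling whole sites is fragile: with the 12 clusters in Protocol 9.3, a given site is missing from (11/12)^12 = 35% of resamples, so a single-site country would drop out of a model that must contain it. The extension's own site count is not stated.
- Keep the crude PAR, by country, as descriptive.

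The cost is modest: SAP wording and one post-estimation step on a planned model, using data already collected (Protocol 6.5.7, 6.5.8, 6.5.13 and 6.6.4.1). The downside is some dependence on the model. If an extension SAP already does this, the sponsor need only confirm it.
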